- Investigator's assessment of the treatment efficacy, OEI-w₂₅ value (per the scale from 1 evident aggravation to 6 significant improvement);
- Assessment of the total number of paracetamol tablets taken per the patient diary (one tablet = 500 mg) starting from day 1, value PARACETAMOL-w₂₅;
- Assessment of the total number of NSAID tablets taken per the patient diary starting from day 1, value NSAID-w₂₅,
- Complete blood count;
- Blood biochemistry: glucose, ALT, AST, ALP, GGTP, total bilirubin, creatinine, uric acid;
- Coagulogram (APTT, PT, prothrombin index, fibrinogen);
- Urine analysis;
- Express urine pregnancy test for women with the preserved reproductive potential;
- AE assessment.
- In case of planned completion of the study and completion of all procedures provided in the clinical study protocol, the patient will be provided with studied medical device NOLTREX regardless of the treatment group to which the patient was assigned. In this case the patient will receive 4 packages of NOLTREX which corresponds to one treatment course.

Unscheduled visit

Unscheduled visits will be made as necessary, for example, in the event of aggravation of the studied medical condition, AE or intolerability of the study MD or placebo therapy. When an unscheduled visit is made, regardless of its reason, the investigator makes the following procedures and completes corresponding eCRF pages (Unscheduled visit):

- Collection of complaints and medical history;
- Recording of concomitant therapy;
- Measurement of body weight;
- Assessment of vital signs (BP, HR, RR, body temperature);

- Physical joint examination;
- Assessment of the patient diary;
- AE assessment.

If clinically indicated and meeting the criteria, any of the study procedures can be additionally made on the unscheduled visit by the decision of the Principal Investigator.

Premature study discontinuation visit

• On the premature study discontinuation visit, the same procedures are made as on Visit 5

Main parameters of efficacy and safety assessment

rs of Primary endpoint – change of the total WOMAC score (WOMAC-T) safety on Visit 5 (Week 25) in comparison with baseline on visit 1 (Week 1).

Secondary endpoints:

- Change of the total WOMAC score (WOMAC-T) on Visit 4 (Week 13) in comparison with baseline on Visit 1 (Week 1);
- Change of the pain subscale score (WOMAC-A) on Visit 3 (Week
 6), Visit 4 (Week 13) and Visit 5 (Week 25) and in comparison with baseline on Visit 1 (Week 1);

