- 30) Severe decompensated chronic or acute diseases and other conditions which, by the opinion of the study physician, may preclude the patient's participation in the study or affect the study results.

Subject exclusion criteria

- Ethics Committee, regulatory bodies or the Sponsor terminate the study or participation of the clinical site in the study for any reasons;
 - Need in paracetamol or NSAID intake due to knee osteoarthritis 4 days a week or more during 2 successive weeks;
 - 3) The investigator makes the decision that a patient should discontinue the study in the best interests of the patient;
 - Informed consent revocation (patient's unwillingness to continue the study);
 - 5) Major deviation from the study protocol;
 - Individual intolerability or contraindications to the study MD, placebo or paracetamol;
 - AE/SAE which requires examination and/or treatment affecting significantly the study procedures (in particular, development of active arthritis or hemarthrosis of the target knee joint);

- 8) Erroneous study inclusion (for example, the patient was included with a violation of the protocol inclusion/non-inclusion criteria);
- 9) A patient has non-inclusion criteria during the study;
- 10) A patient takes/needs additional treatment which can affect the study result or patient's safety (see section "Disallowed concomitant therapy");
- 11) Other conditions or events which require, by the opinion of the study physician, the patient's exclusion from the study.
- 12) Injury of the studied joint.

Disallowed concomitant therapy

- 1. Glucocorticosteroids in any dosage form;
- 2. Any intra-articular or peri-articular injections, physical therapy, as well other therapeutic or rehabilitation measures for knee osteoarthritis, except the study procedures;
- NSAIDs and analgesics including the local ones (except for paracetamol and NSAIDs permitted by the protocol in cases when paracetamol is ineffective);
- 4. Paracetamol intake in dose over 4000 mg a day;
- 5. the use of one of the NSAIDs permitted by the Protocol in doses exceeding those permitted by the Protocol (permitted drugs and doses: diclofenac potassium 50 mg 2 times a day, diclofenac sodium tablets 75 mg 2 times a day, naproxen tablets 500 mg 2 times a day, naproxen sodium tablets 550 mg 2 times a day, meloxicam tablets 7.5 mg once a day, celecoxib tablets 200 mg 2 times a day);
- use of NSAID in combination with paracetamol or combination of two or more NSAID;

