#### 2.1.3 Analysis of secondary efficacy parameters

An analysis of the following secondary efficacy parameters is planned:

- Changing the overall score on the WOMAC scale (WOMAC-T) on Visit 4 (week 13) compared to the basal value on Visit 1 (week 1);
- The change in score on the subscale of pain (WOMAC-A) on Visit 3 (week 6), Visit 4 (week 13) and Visit 5 (week 25) and compared with the basal value on Visit 1 (week 1);
- The change in the score for the stiffness (WOMAC-B) and functionality (WOMAC-C) on Visit 3 (week 6), Visit 4 (week 13) and Visit 5 (week 25) compared to the basal value on Visit 1 (week 1);
- Evaluation of the treatment efficacy by the patient, the value OEP (on a scale of 1 a clear deterioration to 6 a significant improvement) at visits 3, 4 and 5 (OEP-w6, OEP-w13, OEP-w25);
- Evaluation of the effectiveness of treatment by the investigator, the value OEI (on a scale of 1 a clear deterioration to 6 a significant improvement) on visits 3, 4 and 5 (indicators OEI-w6, OEI-w13, OEI-w25);
- Assessment as per patient diary of the total number of paracetamol tablets taken (one tablet = 500 mg) starting on day 1, on visits 3, 4 and 5 (PARACETAMOL-w6, PARACETAMOL-w13 and PARACETAMOL-w25, respectively);
- Assessment per patient diary of the total number of NSAID tablets, starting on day 1, at visits 3, 4, 5 (values NSAID-w6, NSAID-w13 and NSAID-w25, respectively)
- Drop-out rate due to safety (exclusion criteria 2, 3, 6, 7);
- Drop-out rate due to low patient adherence to treatment (criteria 4 and 5).

For secondary efficacy parameters, the following statistical analysis methods are planned:

- For quantitative indicators, an analysis similar to the analysis of the primary endpoint (covariance analysis) followed by the identification of groups with significant differences using Tukey's HSD.
- For frequency indicators (segments) comparison of groups using the  $\chi^2$  criterion ("chi-square").

Analysis of secondary efficacy parameters will be conducted on the ITT population (main analysis) and on the PP population (additional analysis).

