## 2.6 Procedures to count the missing, non-analyzable and questionable data

During the monitoring visits to the clinical center, the monitoring specialists authorized by the sponsor will conduct an analysis of patient's eCRF to identify any lack of necessary data. In the absence of data in the eCRF and the availability of relevant information in the primary documentation, the questions to the investigators and instructions for eliminating the inconsistencies will be formulated.

The statistician, authorized by the sponsor, and the principal investigator, when checking the database of research results, will analyze for the presence of dubious, missing and non-analyzable data, and will also formulate questions to investigators.

Investigators, if possible, will eliminate the identified errors in eCRF and inform the main investigator and authorized representatives of the sponsor about this. If the detected errors in the data cannot be eliminated after the completion of patient participation in the study, the statistical analysis of the data will be used to analyze the sensitivity of the resulting parameters to the doubtful data found. Information about the missing, doubtful and non-analyzable data will be presented in the final clinical trial report.

The missing data for the primary efficacy parameter will be replenished by the last observation carried forward (LOCF) method (transfer of data from the last available observation point to the point for the main analysis).

For the remaining parameters of efficacy, safety and tolerability, data replenishment is not provided.

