## 2.8 Selection of study participants for analysis

#### 2.8.1 Population selected on the basis of prescribed treatment (ITT)

For the ITT data set, also known as the full analysis set (FAS), all randomized participants are included who were treated with the medical device under the study, regardless of the extent to which the protocol was followed during the study. This data set is essential for analyzing primary and secondary efficacy parameters.

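### WOMAC subscales and Week-13 WOMAC-T get no imputation and a single-visit ANCOVA, so their main ITT analyses are observed-case; one repeated-measures model per score is a cheap improvement

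*SAP*

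**What the plan says.** SAP 2.6 treats the endpoints differently. For the primary: "The missing data for the primary efficacy parameter will be replenished by the last observation carried forward (LOCF) method". For everything else: "For the remaining parameters of efficacy, safety and tolerability, data replenishment is not provided". The same section mentions a sensitivity analysis, but for data errors that cannot be corrected, not for drop-out.

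SAP 2.1.3 gives the secondary model: "For quantitative indicators, an analysis similar to the analysis of the primary endpoint (covariance analysis", with the listed changes defined visit by visit. On the analysis set it says: "Analysis of secondary efficacy parameters will be conducted on the ITT population (main analysis) and on the PP population (additional analysis". SAP 2.8.1 defines the ITT set as randomised and treated participants, "regardless of the extent to which the protocol was followed during the study".

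Two protocol passages bear on who is missing and what is known about them. Subject exclusion criterion 2 in the synopsis is: "Need in paracetamol or NSAID intake due to knee osteoarthritis 4 days a week or more during 2 successive weeks". Under the premature discontinuation visit it says: "On the premature study discontinuation visit, the same procedures are made as on Visit 5". Visit 5 includes the full WOMAC.

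**The concern.** Pain, stiffness and function are the first stated study goal. A single-visit ANCOVA without imputation cannot use a patient who has no score at that visit, even if earlier scores exist. The ITT label therefore promises patients whom the model omits. They need not be a random subset, since sustained analgesic need for the knee is itself a reason to leave. If the arms lose such patients at different rates, the subscale contrast is biased.

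There is also a question of coherence. WOMAC-T and its three subscales come from one questionnaire. If the Week-25 total is carried forward and the Week-25 subscales are not, the reported subscale changes need not add up to the reported change in the total, for technical reasons alone.

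**Working it through.** **1. The plan's own sample size.** Inputs (SAP 2.3): f = 0.25, two-sided α = 0.05, power 0.80, 2 groups, 2 covariates. With λ = f²N and denominator df = N − 2 − 2, the smallest adequate N is 128: λ = 0.0625 × 128 = 8.0, df = 124, critical F = 3.9175, power = 0.8014. This reproduces the printed output, and the stated 130 is 128 rounded up. The same formula gives power 0.807 at N = 130 and 0.846 at N = 144.

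**2. Patients analysed at Week 25.** With 144 randomised and 130 completing, 144 − 130 = 14 have no Week-25 score (14/144 = 9.7%). WOMAC-T at Week 25 uses up to 144 through LOCF. It is *up to* because SAP 2.6 does not say whether a baseline value may be carried forward. WOMAC-A, -B and -C at Week 25 use about 130, unless exit scores count as Week 25.

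**3. Weeks 6 and 13.** A patient who leaves in Week 20 still contributes at both visits. These analyses are available-case and lose fewer patients.

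**4. Size of the bias, by arithmetic.** Let p be the share missing in an arm and D how much worse leavers are than stayers, in SD, taken as equal in both arms. Then

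observed-case benefit − all-patient benefit = (p_device − p_placebo) × D.

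The documents give neither D nor the split of exits by arm; D = 0.5 to 1.0 SD is an assumption. The scale is 0.5 SD, since f = 0.25 with two equal groups means d = 2f = 0.5.

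| Leavers of 72, device / placebo | D = 0.5 | D = 1.0 |
|---|---|---|
| 7 / 7 | 0 | 0 |
| 4 / 10 | −0.042 SD | −0.083 SD |
| 2 / 12 | −0.069 SD | −0.139 SD |
| 10 / 4 | +0.042 SD | +0.083 SD |

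For exits of 10% on placebo and 7% on device, the formula gives 0.03 × 0.5 = 0.015 SD to 0.03 × 1.0 = 0.03 SD, or 3–6% of 0.5 SD.

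**5. Size of the bias, by simulation.** Assumptions: 72 per arm, true Week-25 difference 0.5 SD, correlation 0.65 between post-baseline visits, exit driven by the last observed score, more exits on placebo.
- Exits about 9–10% placebo and 6–8% device: observed-case ANCOVA shrinks the effect by roughly 1–6%.
- Exits about 20–22% placebo and 15–18% device: roughly 2–12%.
- A likelihood model using all visits stays near 0.50 in both settings. That is expected, because the simulated exits are missing at random given observed scores.

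Shrinkage is at the low end when baseline is itself strongly correlated with the outcome. It grows with the gap between arms: a 5-point gap with D = 1.0 gives 0.05 SD, or 10% of 0.5 SD.

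**6. Exit scores, two readings.** If they stay at their actual date, an early leaver's subscales are missing at Week 25 while the total is carried forward. If they count as Week 25, a patient who attends the exit visit has all four scores there, and total and parts agree on that patient. The score then describes an earlier time. Neither document chooses.

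**The case against.** The strongest case against is that the plan does state a rule, that observed-case ANCOVA is common for secondary endpoints, and that the effect is small at the plan's own exit rate. Much of this stands, and it rules out several stronger readings.

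- *Every secondary endpoint is affected.* Not so. The two drop-out-rate endpoints are known for all treated patients, and one of them, "Drop-out rate due to safety (exclusion criteria 2, 3, 6, 7"), counts those who leave under criterion 2. Symptom-related exits are therefore visible in the secondary results.
- *All these are completer analyses.* In effect true at Week 25 only.
- *Power is lost against plan.* The design needs 130 completers and has them. The only comparison is with what 144 patients could give.
- *The bias works against the device.* Only if placebo loses more poor responders. It is zero with balanced exits of equal severity and reverses if the device arm loses more.
- *The documents contradict each other on exit scores.* They do not. The protocol says that the procedures are repeated, not that the values are stored as Week 25. This is silence.

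SAP 2.1 also calls itself a brief description and defers detail. That does not answer the point, because 2.6 states a definite rule rather than postponing one. Nor does a mixed model for the subscales alone cure the mismatch with an LOCF total, so the fix has to address that too.

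**Conclusion.** The point holds in a limited form. For WOMAC-A, -B and -C at Weeks 6, 13 and 25 and WOMAC-T at Week 13, the stated rule and model make the main ITT analyses observed-case. Exit can be related to outcome, and no sensitivity analysis for drop-out is planned.

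The expected distortion is small: roughly 1–6% of a 0.5 SD effect (0.005 to 0.03 SD) at about 10% exits, and roughly 2–12% (0.01 to 0.06 SD) at about 20%, which is twice the plan's ceiling. These ranges rest on an assumed correlation, exit mechanism and gap between arms. A very uneven split such as 2/12 with D = 1.0 would give 0.139 SD.

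That the Week-25 total and subscales rest on different patients is conditional on how exit scores are dated. This is a worthwhile, inexpensive improvement to the secondary analyses. It does not undermine the primary result.

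**What to change.** **SAP 2.1.3.** Analyse each WOMAC score with one repeated-measures model over Weeks 6, 13 and 25: treatment, visit, treatment-by-visit, baseline of that score, baseline-by-visit and K-L stage, with unstructured covariance, on all treated randomised patients with any post-baseline score. Read the listed visit contrasts from it. Report the Week-25 WOMAC-T estimate from the same model as a sensitivity analysis to the LOCF primary, so that total and subscales can be compared under one rule.

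**SAP 2.6.** Keep discontinuation-visit scores at their actual date. Assign one to a scheduled visit only within a pre-specified window, and only if that visit has no score. Report N analysed per visit and arm.

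**Cost.** SAP wording and modest programming, settled before database lock; no new data. The model relies on missing-at-random given the observed scores. Exits prompted by phone contacts between visits may depart from that, but the assumption is weaker than the one observed-case ANCOVA needs. The global ratings and cumulative tablet counts are outside this model; the dating rule should say how an early leaver's values are treated there as well.

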## 2.7 Procedures for reporting any deviations from the original statistical plan

The decision to change the statistical plan reflected in this protocol is made by the sponsor.

All changes in the original statistical plan with their justification are reflected in the final report of the clinical study.

## 2.8 Selection of study participants for analysis

#### 2.8.1 Population selected on the basis of prescribed treatment (ITT)

For the ITT data set, also known as the full analysis set (FAS), all randomized participants are included who were treated with the medical device under the study, regardless of the extent to which the protocol was followed during the study. This data set is essential for analyzing primary and secondary efficacy parameters.

#### 2.8.2 Population selected based on compliance with protocol (PP)

Primary and secondary efficacy parameters will additionally be analyzed using a set of data from study participants selected by the protocol compliance principle (PP). The participant will be excluded from the PP data set in the following cases:

- Significant violation of the inclusion and non-inclusion criteria.
- The use of prohibited concomitant therapy.
- Any other significant violation of the protocol, recognized as significantly violating the basic assessment of the efficacy of particular study participant.

#### 2.8.3 Population for safety assessment

The data set analyzed for safety assessment is identical to the ITT data set. However, unlike the population, depending on the treatment prescribed, participants are analyzed depending on the actual medical device received (if it is different from the medical device that was assigned by randomization). All types of safety analysis will be based on the use of a data set for safety assessment.

All decisions regarding the choosing of the databases being analyzed will be made before the research database is closed.

## 3 Data management

## 3.1 Retention of randomization codes and their disclosure procedures

Patient randomization code is stated in documents intended for the use beyond a study site (eCRF, SAE reports, etc.). The assigned patient randomization code is entered to eCRF and corresponding forms. Patient randomization code is not changed during the study.

Randomization plan is kept for control access. The study personnel is responsible for randomization compliance with the established guidelines.

The access to the list of randomization codes will be limited to unblinded Sponsor personnel involved in preparation of randomization table, its implementation to IxRS (if applicable), and responsible for emergency code break. Unblinded personnel will not take part in the study and will not contact with other members of project team and blinded study site representatives.

## 3.2 Description of data handling and recording

All study site records and documents related to the clinical site, as well those in the investigator's file (including informed consent forms, logs, subject accountability sheets, etc.), as well subject source medical documents should be kept for 15 years after the study completion. The study sponsor should control integrity and availability of all clinical study materials for the entire life cycle of the study MD. Archived data can be kept as xerocopies, as well as on optic and electronic information media. The principal investigator should immediately inform the sponsor about the facts of unintended damage/destruction, as well change of the storage location of clinical study materials. The intended destruction of archived materials is possible only with written permission of the study sponsor.

All obtained information including AE/SAE information will be recorded to source documents and then transferred to eCRF. eCRF will not contain data not presented in source documents.

After the completion of scheduled visits by subjects and eCRF filling by the investigator, eCRF will be verified against source documents by the authorized sponsor monitors. If eCRF is completed correctly and precisely in accordance with source document data, the monitor confirms the verification of source documents and eCRF data in eCRF entering the verification flag. If at the stage of data assessment in eCRF, the quality control manager and/or biostatistician have any data questions, all clarifications and changes in eCRF data will be documented via generation of electronic queries for data clarification in eCRF. Responses on such queries are checked by the monitor, as well for compliance of corrected data to query text (if applicable), and, if the answer is deemed sufficient, the query will be closed. Otherwise, the query will be re-opened with additional clarifying text for the investigator.

The investigator should provide information confirming possibility of timely subject enrollment following the criteria provided by the protocol.

The study should be carried out in accordance with the protocol and applicable sponsor standard operating procedures. If it is necessary to introduce changes to the protocol, the procedure stated in Section 4 of the present protocol should be followed.

Investigators should complete source medical documents and eCRF of all subjects included to the study.

The investigator is responsible for complete and accurate eCRF completion. All data recorded in eCRF should be presented in subject's source medical documents in printed form or as records made by the investigator or another authorized person in the clinical site.

In eCRF, in accordance with source documents, all significant details of subject participation in the study are recorded. eCRF should contain data on completion of subject participation in the study. eCRF should be completed within 7 days after subject visit to the study site.

eCRF should be completed in accordance with the instruction on eCRF completion. The errors made should be corrected entering a new value to eCRF, and the old value will be saved in the history of changes (audit trail). All missing data should be explained in eCRF which will be implemented with a special marker field (check mark) confirming missing data. If necessary, the investigator can enter a comment to a corresponding field clarifying reasons for missing data. eCRF should be certified with the electronic signature of the study investigator. The signatures certify that information contained in eCRF is reliable.

All study information and collected data are strictly confidential. The Investigator has right to report the study information to persons directly not taking part in the study, only with the Sponsor permission.

The final report consisting of statistical and clinical report is formed after database lock and completion of statistical processing of the study results.

The final report is signed by the principal investigators of the clinical sites who confirm study results and conclusions, sealing the report with a stamp of the institution.

